8.2.5 Missed Doses

Missed doses will not be replaced during a cycle. If a subject misses more than 2 doses of any cycle for reasons other than toxicity, the subject will be discontinued.

8.2.6 Changes in Body Surface Area (BSA)

Dose adjustments do not need to be made for weight gains/losses of \leq 20%. Subjects with a BSA greater than 2.2 m² should receive a dose based upon a BSA of 2.2 m².

8.2.7 Dosing Modifications

Dose modifications and delays different from those stated in the protocol, for management of toxicities, will be permitted at the discretion of the Investigator.

8.2.8 Safety Considerations

Based upon the experience in the Phase 1 and 2 clinical studies with CFZ, the following observations are noted:

- A "first dose effect" has been seen, which is notable for fever, chills, rigors, and/or dyspnea occurring during the evening following the first day of infusion and an increase in creatinine, which may be the clinical sequelae of rapid tumor lysis and/or cytokine release.
- Should a "first dose" effect occur at any point during Cycle 1 or 2, treatment with high dose glucocorticoids (e.g. methylprednisolone 50–100 mg) is recommended. In addition, intravenous fluids, vasopressors, oxygen, bronchodilators, and acetaminophen should be available for immediate use and instituted, as medically indicated.
- Dexamethasone 8 mg PO/IV will be administered prior to all CFZ doses during the 1st cycle.
- If treatment-related fever, rigors, chills, and/or dyspnea are observed post any dose of CFZ after dexamethasone has been discontinued, dexamethasone should be re-started and administered prior to subsequent doses.
- CrCl changes are mostly transient, reversible, and non-cumulative. All subjects should be well hydrated. Clinically significant electrolyte abnormalities should be corrected prior to dosing with CFZ. Renal function must be monitored closely during treatment with CFZ. Serum chemistry values, including creatinine, must be obtained and reviewed prior to each dose of CFZ during Cycles 1 and 2. Carfilzomib must be held for subjects with a CrCl < 15 mL/min at any time during study participation.
- Subjects with active or suspected infection of any kind that required systemic treatment should not be dosed with CFZ until the infection has resolved and if being treated with anti-infective, the course of antibiotics has been completed.
- Carfilzomib treatment can cause nausea, vomiting, diarrhea, or constipation sometimes requiring the use of anti-emetics or anti-diarrheals. Fluid and electrolyte replacement should be administered to prevent dehydration.

9.0 CONCOMITANT THERAPY

Medications used during the course of the study should be documented.

9.1 Prohibited Concomitant Therapy

- The administration of concurrent medications intended to treat WM or MZL are not allowed during protocol therapy, except plasmapheresis when clinically indicated. Concurrent radiation therapy is prohibited.
- Topical and inhaled corticosteroids to treat other medical conditions are allowed. Intermittent oral or IV corticosteroid administration is allowed as premedication prior to rituximab therapy or carfilzomib in cycle 1 or future cycles if clinically indicated; for management of nausea or vomiting; or for treatment of infusion reactions.

9.2 Patients should be strongly discouraged from taking any "alternative" or "naturopathic" medications since these agents may interact with CFZ. Any use of these medications should be at the judgment of the treating physician and should be documented in the patient's medical record

10.0 STUDY PROCEDURES AND CALENDAR

Pre-entry assessments other than laboratory tests may be done within 6 weeks of enrollment, and need not be repeated within that timeframe. Pre-entry laboratory studies must be done within 14 days of cycle 1.

| Required Studies | Pre-Entry ¹ (within 6 wks of enrollment unless indicated) | Day 1 of Each Cycle, +/- 3 days | Days 8 and 15 of each Cycle, +/- 3 days | Between Cycle 2 Day 15 and Cycle 3 day 1 | Weekly for Cycles 3-6 for all WM Rituximab -treated subjects | End of Treatment (EOT) | Follow -Up |
|---|---|--|--|--|---|------------------------------|----------------|
| Physical | | | | | | | |
| Medical history | X | X ¹¹ | | | | | |
| Physical exam | X | X ¹¹ | | | | X ⁷ | X ⁸ |
| Vital signs including blood pressure (BP, HR, Temp, Respiratory rate) | X | X | X | | | | |
| Performance status | X | | | | | | |
| Response assessment | X | | | X | | X ⁷ | |
| Adverse event assessment | X | X ¹¹ | | | | X ⁷ | |
| Patient home blood pressure monitoring | | Cycle 1 ¹² | | | | | |
| Lab | | | | | | | |
| CBC with differential | X | X ¹¹ | X | | | X ⁷ | X ⁸ |
| Comprehensive metabolic panel | X | X ¹¹ | X | | | | |
| Serum LDH | X | X ¹¹ | | | | X ⁷ | |
| Serum phosphorus | X | X ¹¹ | | | | | |
| for WM: SPEP with m-protein quantification, identification ¹ | X | X ¹¹ | | X | | | X ⁸ |
| for WM: IgM (quantitative) | X | X ¹¹ | | X | X ⁶ | X ⁷ | X ⁸ |
| for WM: Serum viscosity | X | | | | | | |
| B2 Microglobulin | X | | | | | X ⁷ | |
| Bone marrow studies | X ² | | | X (for WM) ⁵ | | X ^{2,7} | |
| Pregnancy test | X ³ | | | | | | |
| Hepatitis B testing | X ⁹ | | | | | X ⁷ | |
| Peripheral blood for flow cytometry | X | | | X ⁵ | | X ⁷ | |

| | | | | | | | |
|---|-----------------|--|--|---|--|----------------|----------------|
| BNP | X | X ¹¹ - cycles 2,4,6 only | | | | | |
| Radiology | | | | | | | |
| CT chest, abdomen and pelvis | X ⁴ | | | X | | X ⁷ | X ⁸ |
| MUGA or echocardiogram ¹⁰ | X ¹⁰ | | | | | | |

1 Pre-entry studies may be performed within 6 weeks of cycle 1 day 1 other than lab studies, which must be done within 14 days of Cycle 1 Day 1 of treatment. Baseline SPEP should be obtained for all patients, but repeat measurements are only required for WM patients.

2 Baseline bone marrow aspirate and biopsy should be performed within 12 weeks of enrollment. Post therapy marrow will be performed only to confirm complete response, or as clinically indicated. Bone Marrow Studies include aspirate and unilateral biopsy with immunohistochemistry, as well as flow cytometry of the aspirate at baseline and after 2 cycles (baseline and post-cycle 2 cycle marrow aspirates are required for correlative analysis for WM patients).

3 Pregnancy test in women of childbearing potential.

4 CT imaging should be performed within 8 weeks of enrollment. CT neck should also be performed, if cervical adenopathy is present on physical exam. CT scans are repeated at interim analysis or during study protocol treatment for patients with nodal/extramedullary disease at baseline. CT scan should be performed in subjects with nodal/extramedullary disease post-therapy to assess response.

5 For WM patients only, post-cycle 2 bone marrow and flow cytometry studies are required for correlative studies but will not be used for response assessment, which relies on SPEP (for WM) and CT imaging (for MZL). Post-cycle 2 studies may be performed any time after C2D15 dose of CFZ, up until Cycle 3 Day 1.

6 For subjects receiving rituximab with WM, weekly quantitative IgM level (+/- 3 days) is to be measured. Further studies (serum viscosity, CBC, chemistries; additional clinical evaluations) may be performed if hyper-viscosity is suspected. Plasmapheresis may be performed as clinically indicated.

7 Post therapy studies should be done 3 - 5 weeks post cycle 6 or after the patient's last cycle, whichever comes first.

8 Follow-up should be done as per the clinical standard of care. A typical schedule includes every 3 months (total follow-up time from start of drug is 1 year). CT imaging as a standard of care surveillance measure should be performed no more frequently than every 6 months, unless a shorter interval is clinically indicated.

9 Hepatitis B core Ab, Hepatitis B surface Ag; further testing as clinically indicated including HBV DNA

10. Measurement of cardiac ejection fraction within 12 weeks of enrollment, by MUGA, echo, or other invasive/noninvasive testing, is allowed.

11. For cycle 1 day 1 only, if history, physical exam, and labs are performed within 14 days of Cycle 1 day 1, they do not need to be repeated. BNP testing results, when associated with dyspnea or signs of cardiac disease, may be used to initiate further testing per investigator judgment.

12. Home blood pressure monitoring at least twice per week will be conducted during cycle 1 for patients with pre-existing hypertension on medical therapy, or any who develop grade 3 hypertension or require the addition of antihypertensive therapy during cycle 1. Patients should record blood pressure on a provided diary during cycle 1. Dosing of CFZ must be held for grade 3 or higher systolic hypertension as per section 8.2.4

11.0 CRITERIA FOR EVALUATION AND ENDPOINT DEFINITIONS

(See Appendix 20.3, and References 25,26, and 38)

Diagnosis and response criteria are to be based on International Workshop³⁶, Lugano response criteria²³, and criteria of Matute et al²⁴ for patients with splenomegaly alone.

For WM, SPEP with m-protein quantification should be the primary means for assessing response to therapy, in addition to imaging, repeat immunofixation (to confirm CR), and marrow aspirate and biopsy when indicated. (Note that quantitative IgM by nephelometry is to be used for determining rituximab flare, as results may be available more rapidly.)

12.0 STATISTICAL CONSIDERATIONS

12.1 Accrual: We anticipate accrual of 24 patients over 18 - 24 months. Accrual will be limited to the first 9 patients initially then paused -- if needed-- to ensure the stopping rule (section 12.2 and 12.3) has not been reached before additional patients are accrued.

12.2 Sample Size: This is a Simon 2 stage (minimax) design with stopping for futility. The primary endpoint is overall response rate, measured after 2 cycles of therapy. This model requires 24 total patients to be assessable after 2 cycles.

The null hypothesis, that the true response rate of single agent CFZ is 25%, will be tested against a one-sided alternative. In the first stage, 9 subjects will be enrolled. If two or fewer patients responds, the study will be stopped for futility. If 3 or more respond, a total of 15 more subjects will be enrolled. The null hypothesis will be rejected if 10 or more responses are observed in 24 assessable subjects. This design yields a type I error rate of .05, and a power of 80%, when the true response rate after 6 cycles of CFZ is 50%.

Descriptive statistics will be used for baseline characteristics, and responses to treatment. Changes in mean fluorescence intensity pre- and post-CFZ of both CD20 and CD19 will be assessed compared using paired T testing.

Estimate time to best response, time to progression, and survival outcomes for subjects using Kaplan-Meier analysis.

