The approved dose of CFZ for relapsed/refractory multiple myeloma is as follows, and employs a priming dose and if tolerated, then escalating to 27 mg/m² (over 10 minutes) when given in combination with lenalidomide and dexamethasone, or escalating CFZ to 56 mg/m² (given over 30 minutes) when given in combination with dexamethasone:

- o CFZ in combination with lenalidomide and dexamethasone
 - o cycle 1: 20 mg/m² over 10 minutes on days 1 and 2; if tolerated, increase dose to 27 mg/m² over 10 minutes on days 8, 9, 15, and 16 of a 28-day treatment cycle
 - o cycles 2-12: 27 mg/m² over 10 minutes on days 1, 2, 8, 9, 15, and 16 of a 28-day treatment cycle

- o cycles 13-18: 27 mg/m² over 10 minutes on days 1, 2, 15, and 16 of a 28-day treatment cycle
 - CFZ in combination with dexamethasone
- o cycle 1: 20 mg/m² over 30 minutes on days 1 and 2; if tolerated, increase dose to 56 mg/m² over 30 minutes on days 8, 9, 15, and 16 of a 28-day treatment cycle
- o cycle 2 and onwards: 56 mg/m² over 30 minutes on days 1, 2, 8, 9, 15, and 16 of a 28-day treatment cycle

Results of CFZ for first-line treatment of WM in combination with rituximab and dexamethasone have recently been published in abstract form. The combination produced a response in 81% of patients, and 22/31 remain on study at 8 cycles of therapy; no neuropathy of grade 2 or higher was seen.¹² However, the single-agent efficacy of CFZ in WM or other NHL is undefined, nor have response-adapted studies--reserving combination therapy with rituximab for non-responders-- been reported.

The dosing of carfilzomib has recently undergone evolution, with implications for patient convenience and the practical administration of therapy. CFZ was historically administered twice weekly, but recent data from multiple myeloma (MM) identified acceptable safety and promising efficacy once weekly administration at the so-called 20/70 dose (CFZ 20 mg/m² over 30 minutes on Cycle 1 Day 1, then 70 mg/m² on D8 and D15 of cycle 1 and all days of future cycles; cycles are repeated every 28 days).¹⁵ In that study, only 12% of patient discontinued therapy due to adverse events. Despite limitations of cross-trial comparisons, adverse event rates were similar or lower than prior twice-weekly studies. This data, in addition to providing the basis for a large upcoming study using weekly carfilzomib in myeloma (NCT#02412878), support the proposed weekly dosing in this trial.

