5.0 ELIGIBILITY CRITERIA

Patients with Waldenström Macroglobulinemia or Marginal Zone lymphoma who meet inclusion/exclusion criteria below are eligible.

At least 5 patients with rituximab-refractory disease will be enrolled (best response of stable disease or progression while on treatment with, or progression within 6 months of, rituximab-containing therapy). Accrual will be modified to ensure 5 rituximab-refractory patients are enrolled, without enrolling more than 24 total patients.

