7.1.1 Dose and Administration

Subjects with a BSA greater than 2.2 m² should receive a dose based upon a BSA of 2.2 m².

Carfilzomib will be administered 20 mg/m² over 30 minutes on Cycle 1 Day 1. If tolerated, the dose will be increased to 56 mg/m² on D8 and D15 of cycle 1. Escalation to 70 mg/m² starting with cycle 2 and beyond is allowed for all patients who have met criteria for ongoing therapy without delay due to toxicity, or need for dose modification as described in section 8.0. Cycles are repeated every 28 days. Do not administer as an IV bolus.

A maximum of 6 total cycles may be given.

7.1.1.1. If 20 mg/m² is not tolerated, it may be repeated with additional supportive care at clinical discretion for up to 4 weekly doses (C1 D1, C1 D8, C1 D15, and C2 D1) while reconsidering dose escalation. CFZ must then be escalated to 56 mg/m² for at least 2 doses, prior to increasing to 70 mg/m² as tolerated.

| Carfilzomib Therapy: Day 1, 8, and 15 of 28-day cycles | |
|---|--|
| Carfilzomib | Cycle 1-6 (actual dates may vary +/- 3 days) |
| Carfilzomib 20 mg/m ² over 30 minutes *with dexamethasone pre-medication | Cycle 1 Day 1 |
| Carfilzomib 56 mg/m ² over 30 minutes *with dexamethasone pre-medication for cycle 1 | cycle 1 Day 8 and 15 |
| Carfilzomib 70 mg/m ² over 30 minutes | All future days starting with Cycle 2 Day 1. |

Dose modification in response to toxicity is described under section 8.0 below.

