7.2 Administration of Rituximab to CFZ Non-responders

Subjects who fail to achieve at least a 25% M-protein reduction based on SPEP m-protein quantification for WM, or partial response for MZL based on imaging, following 2 cycles of CFZ therapy will receive rituximab concurrent with CFZ.

7.2.1 Note: the bone marrow aspirate / biopsy after cycle 2 is exploratory and not to be used for response assessment or determination regarding rituximab.

7.2.2 IV Rituximab, pre-medications, and hypersensitivity management will be administered according to standard institutional or pharmacy guidelines.

| RITUXIMAB weekly x 4 doses (cycle 3) then monthly (cycles 4-6) | | | | |
|---|---|------|------|------|
| Treatment | Cycle 3-6 for patients not responding to CFZ (actual dates may vary +/- 3 days; cycle timing refers to CFZ) | | | |
| | C3 D1,8,15,22 | C4D1 | C5D1 | C6D1 |
| Rituximab 375 mg/m ² | X, X, X, X | X | X | X |

7.2.3 Following rituximab administration for WM, weekly laboratory evaluation of IgM levels (to evaluate for Ig M flare for clinical and study data purposes) is required. (See section 10, study calendar). As clinically indicated, viscosity measurement and other evaluation or management of hyper-viscosity syndrome, including plasmapheresis, should be undertaken. Weekly evaluation will continue until no longer clinically indicated.

7.3 Criteria for removal from protocol treatment: (Note: Subjects discontinued from CFZ will not receive rituximab on study.)

7.3.1 Symptomatic progression of disease after completion of at least 4 total cycles of CFZ therapy (with or without rituximab). IgM flare following rituximab (even if requiring plasmapheresis), or biochemical progression alone do not require removal from protocol treatment.

- 7.3.2 Inability to tolerate more than 20 mg/m² of CFZ during the first 4 doses of therapy, despite maximal supportive care.
- 7.3.3 Development of excess hematologic toxicity not responding to supportive care or persisting despite dose reductions—as outlined in Section 8.0
- 7.3.4 Development of any other unacceptable toxicities unless prophylactic measures can be taken for subsequent cycles.
- 7.3.5 Missed doses will not be replaced during a cycle. If a subject misses more than 2 doses of any cycle for reasons other than toxicity, the subject will be discontinued.
- 7.3.6 Delay of a treatment cycle for more than 4 weeks due to adverse events

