18.0 TERMINATION OF THE STUDY

Patients may be removed from this study at any time per their discretion. Individual patients may be removed from this protocol if they develop any untoward side effects from the study treatment or for other reasons as described under section 7.7.

The study will be closed to accrual upon treatment of the total planned number of study subjects. The study will be completed following treatment of all study subjects and completion of follow-up and data analysis as described in the protocol. If the study drug becomes unavailable for any reason, the study will be suspended until drug availability resumes or terminated as appropriate. In addition, there are stopping rules in place for lack of efficacy as detailed in the statistical section. The Principal Investigator may terminate the study at any time. The IRB and FDA also have the authority to suspend or terminate the study should it be deemed necessary.

The Principal Investigator shall provide Amgen with a final study report no later than **one (1) calendar year** after study completion. The report shall include all AEs generated by the Study, irrespective of whether the AEs are serious or non-serious, and a causality assessment for each AE, regardless of whether the AE is related to the investigational drug.

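### Section 12.2 needs 24 patients assessable after 2 cycles while section 5.0 caps enrolment at 24, so one unassessed early loss leaves the primary test without an applicable rule

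*Combined protocol and SAP*

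**What the plan says.** Section 12.2 describes a Simon two-stage minimax design with response after 2 cycles as the primary endpoint. On the denominator it says: "This model requires 24 total patients to be assessable after 2 cycles". The final rule is: "The null hypothesis will be rejected if 10 or more responses are observed in 24 assessable subjects". The first stage is counted by enrolment: "In the first stage, 9 subjects will be enrolled". Fifteen more follow if at least 3 respond, which makes 24.

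The total is fixed elsewhere too. Section 5.0 secures the rituximab-refractory quota "without enrolling more than 24 total patients", the schema gives N=24, and section 18.0 says: "The study will be closed to accrual upon treatment of the total planned number of study subjects".

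Section 7.3 provides for removal before the cycle-2 assessment. Item 7.3.2 covers a patient unable to go above 20 mg/m² "of CFZ during the first 4 doses of therapy, despite maximal supportive care". Section 7.1.1.1 lets the 20 mg/m² dose be repeated "for up to 4 weekly doses (C1 D1, C1 D8, C1 D15, and C2 D1) while reconsidering dose escalation". Items 7.3.3 to 7.3.6 and 7.3.8 cover toxicity, missed doses, delay and withdrawal.

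The plan does not define assessable. It gives no replacement rule, no rule for a missing cycle-2 assessment, and no cut-off for fewer than 24.

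**The concern.** A plan that needs 24 assessable patients and may enrol only 24 has no room for a loss, yet this protocol foresees losses. On schedule, the four doses in 7.3.2 end at C2D1. The section 10 calendar puts the response assessment between C2D15 and C3D1, so an intolerant patient would normally leave before it. Such a patient also has an End of Treatment response assessment in the calendar, and 12.2 does not say whether that counts. The patient could be scored as a responder, as a non-responder, or left out.

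Three things are at stake. First, 9 responses in 23, for example, would have no prespecified verdict, and the denominator and cut-off would be settled after open-label results are known. Second, leaving out patients who failed through intolerance makes the response rate look better than it was among those treated. Third, the interim look is exposed: with 2 responders and 1 unassessed patient among the first 9, the plan does not say outright whether the study stops or waits for a ninth assessable patient.

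**Working it through.** **Inputs from 12.2.** Null rate 0.25; alternative 0.50; 9 patients in stage 1, stopping at 2 or fewer responses; 24 in total, rejecting at 10 or more. I take 0.50 as the rate at the 2-cycle endpoint. 12.2 attaches it to 6 cycles, which is a separate matter.

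**Formula.** With n assessable, cut-off r and response rate p:

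R(p, n, r) = Σ over x = 3 to 9 of Bin(x; 9, p) × P[Bin(n − 9, p) ≥ r − x].

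**Step 1: the plan's own figures.** R(0.25, 24, 10) = 0.0485 and R(0.50, 24, 10) = 0.8055. The stated 0.05 and 80% are reproduced. An exhaustive search finds no two-stage design with fewer than 24 patients that meets both limits, so the design has nothing to spare.

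**Step 2: chance of at least one early loss,** 1 − (1 − d)^24. The documents give no early-loss rate, so d is assumed.

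| d | 2% | 4% | 8% | 12% |
|---|---|---|---|---|
| P(at least 1 of 24) | 0.384 | 0.625 | 0.865 | 0.953 |

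The only related figure is in section 2.1: "In that study, only 12% of patient discontinued therapy due to adverse events". It covers adverse events over the whole of treatment, in myeloma, so it is a high anchor for toxicity losses in two cycles.

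**Step 3: losses left out, interim look on the first 9 assessable.** Reading A takes 25% and 50% as rates among assessable patients. Reading B takes them as rates among all 24 treated, with lost patients non-responders, so p = 0.25 × 24/n = 6/n or 0.50 × 24/n = 12/n.

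| Assessable n | 23 | 22 | 21 |
|---|---|---|---|
| Cut-off 10, type I error, A | 0.037 | 0.028 | 0.020 |
| Cut-off 10, type I error, B | 0.049 | 0.048 | 0.048 |
| Cut-off 10, power, A | 0.766 | 0.715 | 0.653 |
| Cut-off 10, power, B | 0.822 | 0.838 | 0.852 |
| Cut-off 9, type I error, A | 0.082 | 0.066 | 0.051 |
| Cut-off 9, type I error, B | 0.103 | 0.105 | 0.106 |

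On reading A, a cut-off of 9 gives power 0.845 at n = 23 and 0.816 at n = 22. So at 23 or 22 neither cut-off keeps type I error at or below 0.05 together with power of at least 0.80.

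**Step 4: the single loss falls in stage 1, bounds unchanged.** With 8 then 15 assessable, the sum runs over x = 3 to 8 of Bin(x; 8, p) × P[Bin(15, p) ≥ 10 − x]. Power is 0.733 at p = 0.50 (A) and 0.791 at p = 12/23 (B).

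**Step 5: effect on the reported rate.** Ten responses are 10/24 = 41.7% of treated patients, but 10/21 = 47.6% if three losses are left out.

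**The case against.** The best counter-argument is that little changes in practice. With the cut-off of 10 kept, a lost patient who is left out and one scored as a non-responder both add nothing to the count; only the interim look can differ. If 50% holds only among patients who reach the assessment, leaving losses out gives average power 0.785, 0.763, 0.710 and 0.648 at early-loss rates of 2%, 4%, 8% and 12%. Scoring them as non-responders among 24 gives slightly less: R(0.50(1 − d), 24, 10) = 0.779, 0.751, 0.689 and 0.621. This stands. The proposed wording is not a remedy for power.

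Sections 7.4 and 12.3.1 also phrase the futility rule as responses among the first 9 patients after cycle two. On a plain reading, a patient with no such response has not responded. That eases the interim question, but the final rule still counts assessable subjects.

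Three stronger readings are tempting, and the documents do not support them:

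- *Any dropout breaks the test.* Progression has its own response category and would normally be a non-response. A patient who leaves early may also have Day 1 SPEP results or an End of Treatment assessment.
- *Type I error is inflated.* It is not with the only cut-off the plan gives. The inflated figures need someone to lower the cut-off to 9, which no section permits. Even then the excess on reading A shrinks to 0.051 at n = 21.
- *Power necessarily falls below 80%.* That holds on reading A. On reading B, with nine assessable patients at the interim look, power exceeds 0.80.

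The cap in 5.0 does sit in the sentence on the rituximab-refractory quota, but its words cover total enrolment and agree with N=24 elsewhere.

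**Conclusion.** The point holds as a gap in the decision rule. After one unassessed loss within the cap, the stated test cannot be applied as written, and the plan does not say what replaces it. The power effect is conditional. On reading A it is about 4 percentage points for one loss in stage 2 (0.806 to 0.766), about 7 for one in stage 1 (0.733), and 15 for three losses (0.653). On reading B there is no shortfall, except a slight one (0.791) if stage 1 is judged on 8 patients. Type I error stays below 0.05 while the cut-off is 10; the figures for a cut-off of 9 show only why the rule should be fixed in advance. How often this would arise rests on assumed loss rates, but even 2% gives a 38% chance of at least one loss.

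**What to change.** In 12.2, replace the sentence that requires 24 assessable patients with wording such as: *Every patient who receives CFZ counts, in order of enrolment, among the first 9 and among the 24. A patient without a post-cycle-2 response assessment is a non-responder. Treated patients are not replaced.* Keep the cut-off of 10, change assessable to treated in the rejection rule, and state that 25% and 50% are rates among all treated patients. The cap in 5.0 can stay.

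This needs no extra patients or procedures. Its downside is that a loss unrelated to disease counts as a failure. It makes both stages applicable, keeps type I error at or below 0.0485, and gives a response rate that no longer omits intolerant patients. It does not restore power. Section 12.2 should say that if 50% holds only among patients who reach the assessment, power is about 0.78, 0.75, 0.69 or 0.62 at assumed early-loss rates of 2%, 4%, 8% or 12%. Recovering 80% in that case would need more than 24 patients.
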